To improve retention, *all* participants will receive the AR intervention and be followed for an additional 3 months. One exploratory objective of this study is to examine whether dose-response effects are present when the AR program is re-administered 3 months later. The effects of the AR received as a booster vs. AR received for the first time on AB and body composition will be examined. Given that ABs to social threat appear to be more pronounced in adults with LOC eating compared to those without LOC eating (62, 63), the second exploratory aim is to examine the moderating effects of AB to social threat on intervention effects. The third exploratory aim is to examine the LOC status (LOC vs. No-LOC girls) as a moderator of changes in AB, neural responsivity, food intake, and body composition following the AR program. Finally, given the increase in obesity among Black youth and some findings indicating that Black girls consume more in laboratory meals (45), the fourth exploratory objective is to explore the moderating effects of race on the study outcomes.

V. Specific Aims

Specific Aim #1: To examine the impact of a 2-week AR or control program on AB in overweight girls with and without LOC.

Hypothesis 1: Youth randomized to AR will demonstrate a reduction in AB to palatable foods compared to those in the control condition in: **(A)** The laboratory based on visual probe task and eye tracking; **(B)** The natural environment based on smartphone data.

Specific aim #2: To examine changes in neural responsivity following a 2-week AR or control period in overweight girls with and without LOC.

Hypothesis 2A: Youth randomly assigned to AR will have improvements in “bottom-up” attention circuitry in response to palatable food images (striatum) during UCR: AR will lead to less activation, whereas there will be no change in “bottom-up” attention circuitry in youth given the control condition.

Hypothesis 2B: Youth randomly assigned to AR will have improvements in “top down” attention circuitry (dorsal ACC, vIPFC, dlPFC) during AD: AR will lead to greater activation, whereas there will be no change in “top down” attention circuitry in girls given the control condition.

Specific aim #3: To examine the effect of AR on food intake and body composition.

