Specific Aim 2: Examine changes in neural responsivity following a 2-week attention retraining or control period.

- i. **Primary outcomes:** Change in neural activity during attention bias task paradigm at the baseline laboratory visit vs. post-EMA visit.
- ii. **Secondary outcomes:** Neural activity during the social threat AB task.

Specific Aim 3: Examine the effect of attention retraining on food intake and body composition.

- i. **Primary outcomes:** Change in the energy intake at the buffet meal, change in adiposity/body composition (DXA) from the baseline visit to the post-EMA visit.
- ii. **Secondary outcomes:** Change in self-reported eating patterns (EDE), number of LOC episodes measured via EMA and clinical interview,

Exploratory Aim 1: Examine whether dose-response effects are present for attention bias to palatable foods and body composition in participants who receive the attention retraining program at 3 months as a booster compared to those who receive it for the first time.

- i. **Primary outcomes:** Change in laboratory measured attention bias (i.e., reaction times to palatable foods at the baseline laboratory visit vs. the post-EMA visit), adiposity/body composition (DXA)
- ii. **Secondary outcomes:** Change in EMA-measured attention bias over time (2-week period), self-reported eating patterns (EDE), number of LOC episodes measured via EMA and clinical interview.

Exploratory Aim 2: Examine ABs to social threat (measured as reaction time, eye tracking, and neural activation on the AB to social threat visual probe task at baseline), and potential moderating effects of AB to social threat on intervention effects.

- i. **Outcomes:** Change in energy intake at the buffet meal, adiposity/body composition (DXA).

Exploratory Aim 3: Examine LOC status (LOC vs. No-LOC) on primary outcomes.

- i. **Outcomes:** Change in neural activity during attention bias task paradigm at the baseline laboratory visit vs. post-EMA visit, change in laboratory measured attention bias (i.e., reaction times to palatable foods at the baseline laboratory visit vs. the post-EMA visit), change in food intake, change in adiposity/body composition (DXA)

Exploratory Aim 4: Examine effects of race on primary outcomes.

- a. **Outcomes:** Laboratory measured attention bias (i.e., reaction times to palatable foods at the baseline laboratory visit vs. the post-EMA visit), the energy intake at the buffet meal, adiposity/body composition (DXA).

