and transformation will be applied to obtain oscillatory power estimates. Oscillatory power activity will be calculated by subtracting the baseline activity (1000ms immediately prior to stimulus onset) from the activity evoked during the UCR and AD periods, respectively (84). The synthetic aperture magnetometry (SAM) beamformer technique (161) will be applied to produce a 3D representation of brain activity by calculating the oscillatory power activity for individual voxels (7 mm). Using the anatomical MRI, normalized SAM data will be co-registered and transformed into Talairach space in AFNI software. Based on our hypotheses, a priori brain regions will be selected for examination. Pseudo F-ratios – an index of 3D oscillatory power activity – for the regions-of-interest will be used in analyses (see **Appendix 9**).

3. EMA data will be collected using a specialized platform designed to collect EMA on mobile devices. Data are collected in a local database and transmitted to the Cloud Server in real time. Participant and study profiles are created on the Server and exported from the Server by an administrative user. On this platform, the estimated internal reliability of mean RT computed using split-half r is >.95 (156, 157).
4. *Missing Data and Attrition:* AR and control will be compared on study completion vs. early termination using logistic regression controlling for age, sex, race, lean mass, adiposity, and height (“covariates”). Multiple imputation based upon fully conditional Markov chain Monte Carlo modeling (162) will be used to impute missing data on non-EMA assessments. Primary analyses will be based upon imputed data except for EMA analyses. Sensitivity analyses will use all available data (i.e. no imputation) and maximum likelihood imputation and results will be compared across methods. Although data preprocessing and analytic methods can mitigate artifacts to some extent, excessive participant movement remains a problem. Structural MRI / MEG will be excluded if there is movement > 2.5 mm during respective sessions. At NIH, pediatric fMRI / MEG studies typically have 30-40% attrition in youth due to excessive movement. Thus, attrition rate of 35% is assumed in power analyses.

Primary Analyses:

Specific Aim 1

- a. **Hypothesis 1:** Youth randomized to AR and control conditions will be compared on:

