1. Post-smartphone program lab visit and the 3-month follow-up visit reaction time data from dot probe task will be using a general linear model (or appropriate generalized linear model depending upon distribution diagnostics) controlling for baseline visit reaction time data from dot probe task, and covariates (order effects, age, race, and BMIZ).
2. Reaction time data from EMA

Specific Aim 2

- a. **Hypothesis 2:** General linear model adjusting for baseline neural activity and covariates (order effects, age, race, and BMIZ), will be used to analyze

1. Post-smartphone visit and 3-month follow-up visit neural activity in response to palatable food cues in the “bottom-up” attention circuitry (ventral ACC, OFC, insula, and striatum) in the unconscious reaction period.
2. Post-smartphone visit and 3-month follow-up visit neural activity in response to palatable food cues in the “top-down” attention circuitry (dorsal ACC, vLPFC, dlPFC) in the attention deployment period.

Specific Aim 3

- a. **Hypothesis 3A:** Youth randomized to AR and control groups will be compared on
 1. Post-smartphone program lab energy intake from laboratory test meal using a general linear model (or appropriate generalized linear model depending upon distribution diagnostics) controlling for the baseline visit energy intake and covariates
 2. The daily number of LOC episodes using a generalized estimating equations (GEE) model with a negative binomial response function controlling for baseline LOC episodes and covariates. The model will include a main effect for group, and a group-by-time interaction. Analyses use all available data (no imputation). We will also examine LOC as a continuous daily dependent variable (mean of 3 LOC items).
 3. BMI and adiposity at the 3-month follow-up visit using a general linear model (or appropriate generalized linear model depending upon distribution diagnostics) controlling for baseline lab visit and the post-smartphone program lab visit BMI and adiposity.

Exploratory Aim 1

- a. Youth randomized to AR (who receive the AR program at 3 months as a booster) will be compared to controls (who receive AR for the first time) at post-booster visit and the 6-month follow-up visit on BMI, adiposity, and energy intake using a general linear model (or appropriate generalized linear model depending upon distribution diagnostics) controlling for Visit #2 measurement

Exploratory Aim 2

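### Three sections of the plan disagree on the region and visit that decide Hypothesis 2A, and none names a deciding test

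*Combined protocol and SAP*

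**What the plan says.** Section V, Hypothesis 2A, names one region and one direction for the early, unconscious-reaction (UCR) period: "attention circuitry in response to palatable food images (striatum) during UCR: AR will lead to less activation".

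Section VII.c, Specific Aim 2, gives the primary outcome as "Change in neural activity during attention bias task paradigm at the baseline laboratory visit vs. post-EMA visit". That is one post-baseline visit, and no region is named.

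Section VII.f, Primary Analyses, Specific Aim 2, item 1, analyses "Post-smartphone visit and 3-month follow-up visit neural activity in response to palatable food cues" and specifies the bottom-up "attention circuitry (ventral ACC, OFC, insula, and striatum) in the unconscious reaction period". That is four regions at two visits. Item 2 does the same for the top-down "attention circuitry (dorsal ACC, vLPFC, dlPFC) in the attention deployment period", the same three regions that Hypothesis 2B lists. The widening of the region list is therefore confined to 2A.

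Section VII.f, Preliminary Analyses, item 2, says that regions are chosen in advance from the hypotheses and that values "for the regions-of-interest will be used in analyses", with a reference to Appendix 9. That appendix was not supplied. Nothing in the supplied text states an alpha, a multiplicity adjustment, an order of testing, or a rule for combining regions or visits.

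**The concern.** The hypothesis and its analysis differ on region (section V against VII.f). The primary outcome and the analysis differ on visit (VII.c against VII.f). With no rule for which result counts, a difference in the insula at 3 months could be reported as support for a hypothesis that named only the striatum. Nothing in the plan would mark that as a departure.

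Aim 2 is the trial's mechanistic claim. It sits among the specific aims, apart from the exploratory ones, and carries directional predictions and a primary outcome. About 52 girls are expected to give usable data, so a chance finding in one region could be read as evidence of mechanism.

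**Working it through.** **The plan's own figure.** The sample-size paragraph of VII.f gives 80 randomised, 35% unusable data and more than 80% power for medium to large effects, sized on Aim 1.
- 80 × (1 − 0.35) = 52, or 26 per arm if allocation is 1:1 (assumed; the ratio is not stated).
- At d = 0.80 and an assumed two-sided 0.05, a t test has power 0.81. The claim reproduces at the large end, for one unadjusted test.
- At d = 0.50 power is 0.42, and at d = 0.61 it is 0.58, before any gain from baseline adjustment.
- No power or error calculation is given for Aim 2.

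**The sections side by side, for 2A**

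| Place | Region | Visit |
|---|---|---|
| V, Hypothesis 2A | Striatum | Not separated |
| VII.c, Aim 2 primary outcome | None named | Post-programme only |
| VII.f, Primary Analyses | Ventral ACC, OFC, insula, striatum | Post-programme and 3 months |

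Sections V and VII.c together point to the striatum at the post-programme visit, but no section says that this test decides 2A.

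**Number of tests, if each region has its own model at each visit (assumed)**
- 2A: 4 at the post-programme visit; 4 × 2 = 8 over both visits.
- All of Aim 2: 4 + 3 = 7 at the post-programme visit; 7 × 2 = 14 over both.

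**Chance of at least one false positive, two-sided 0.05 per test (assumed)**

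For k independent tests it is 1 − 0.95^k:
- k = 4: 1 − 0.8145 = 18.5%
- k = 7: 1 − 0.6983 = 30.2%
- k = 8: 1 − 0.6634 = 33.7%
- k = 14: 1 − 0.4877 = 51.2%

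For tests with common pairwise correlation ρ it is 1 − ∫ φ(u) [Φ((1.96 − u√ρ)/√(1 − ρ)) − Φ((−1.96 − u√ρ)/√(1 − ρ))]^k du.

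| Tests | ρ = 0 | 0.3 | 0.5 | 0.7 |
|---|---|---|---|---|
| 2A, post-programme visit (4) | 19% | 17% | 16% | 13% |
| 2A, both visits (8) | 34% | 30% | 25% | 19% |
| Aim 2, post-programme visit (7) | 30% | 27% | 23% | 18% |
| Aim 2, both visits (14) | 51% | 44% | 35% | 25% |

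The correlations are assumptions; the documents give none. With separate between-region and between-visit correlations, each up to 0.7, the two-visit ranges change little: 21–34% for 8 tests and 28–51% for 14.

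**Predicted direction only.** Hypothesis 2A predicts a decrease, so only half of each test's 5% would count as support. For independent tests:
- k = 4: 1 − 0.975^4 = 9.6%
- k = 8: 1 − 0.975^8 = 18.3%

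The matching rate for a single named test is 2.5%.

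**The case against.** A reader might infer that Aim 2 runs 14 unadjusted primary tests, so that a spurious neural effect is likely. The documents do not support that.
- VII.c limits the primary outcome to one visit, which gives 7 tests for Aim 2 and 4 for 2A.
- The plan never says that each region gets its own model. Its reference to activity in a circuit also allows a circuit-level summary.
- Even with 14 tests, the risk passes one half only if all are independent. Regions of one circuit, measured in the same girls, probably are not.
- Alpha is unstated, and Appendix 9 may hold a correction. The most that can be said is that no error control appears in the supplied text.

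The wider region list also has a basis in the protocol. The Introduction's passage on neurocircuitry and LOC eating ties the insula, ACC, OFC and striatum to the early response, so the single region in Hypothesis 2A may be an incomplete list. However, the earlier Introduction section on attention bias and its neurocircuitry assigns the early response to medial temporal and striatal circuitry and puts the ACC and OFC under attention deployment. The background therefore does not settle which list was meant.

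Finally, the trial calls itself a pilot and is sized on Aim 1. This makes strict correction across all regions hard to justify. It does not explain why three sections describe the deciding comparison differently.

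These points limit the size of the problem. The contradiction stands, and a correction in Appendix 9 would not by itself resolve it.

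**Conclusion.** The concern holds as an inconsistency with a material effect on error. Sections V, VII.c and VII.f do not agree on the region or visit that decides Hypothesis 2A, and several different results could be reported as support for it.

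Against a nominal 5%, the chance of at least one false positive for 2A is about 13–19% on the narrower, one-visit reading and 19–34% on the two-visit reading. Support falsely claimed in the predicted direction runs at about half that. Every scenario examined is more than twice the nominal rate, but only the extreme case of 14 independent tests reaches one half.

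These figures rest on two-sided 0.05 per test, one model per region and visit, and correlations from 0 to 0.7, none of which the documents state. The mismatch between sections rests on no assumption.

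**What to change.** - **2A.** State in VII.f that 2A is decided by striatal activity in the UCR period at the post-smartphone visit, adjusted for baseline as planned, and state alpha and sidedness. This follows sections V and VII.c, and the named test loses no power. If the four-region list is what was intended, name one circuit summary or one joint test instead and amend Hypothesis 2A to match.
- **Secondary.** Label ventral ACC, OFC, insula (unless they enter that joint test) and all 3-month neural contrasts as secondary, reported with estimates and intervals. Nothing is dropped; these results lose only their primary status.
- **2B.** Make the post-smartphone visit primary here too. Adjustment across the three regions, by Holm or a single circuit summary, is optional in a pilot. If Holm is used, state its price. The first step tests at 0.05/3 = 0.0167, and with 26 per arm and no covariate gain, per-region power there falls from 0.81 to 0.66 at d = 0.80 and from 0.42 to 0.26 at d = 0.50.
- **Consistency.** Align VII.c with these choices, and move into VII.f any error control now held in Appendix 9.

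The cost is a few lines of text, which should be settled before neural data are compared by arm.

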Loss of control (LOC) eating is a distinct behavioral phenotype in youth (36) and it is associated with AB toward highly palatable food (40, 49, 54), adiposity (37, 38), and weight gain over time (39, 40). Attention bias (AB) involves complex cognitive processes, unconscious reactions (UCR) and attention deployment (AD) (33, 34), each associated with unique neural correlates, best measured using high spatial resolution and temporally sensitive methods (35). Understanding the differences in neurocognitive mechanisms of AB to highly palatable food in youth with LOC eating compared to those without will help inform tailored treatments. These youth may also be at higher risk of AB to social threat, thus examining neurocognitive processes associated with appraisal of socially threatening cues may further the understanding of distinct subtypes of obesity. In the proposed study, we will examine the differences in neurocognitive responding to cues of highly palatable foods in youth with and without LOC eating using MEG, which offers both high spatial resolution and excellent temporal sequencing (84). It is also unknown how these neurocognitive processes are affected by an intervention aimed at modifying AB. Using MEG, the proposed study will elucidate the neurocognitive mechanisms of AB in youth with LOC eating, prior to and following a novel, age-appropriate intervention aimed at modifying AB. Additionally, we will explore whether AB to social threat is more pronounced in overweight youth with LOC compared to those without, and whether, if present, it moderates response to intervention.

IV. Study Objectives

Primary objective

No study to date has examined the impact of AR delivered in the natural environment on AB in a targeted group of youth specifically prone to ABs. Similarly, no study has examined the effect of AR on neurocircuitry of ABs to food using MEG. Overweight adolescent girls (age 12-17y) with and without LOC eating will be studied at baseline and again after completion of a 2-week double-blind, randomized controlled trial of AR away from palatable (trigger) foods. The longer-term effects of AR on AB, neural responding, food intake, and body composition will also be examined at 3-month follow-up.

Secondary objectives (Exploratory)

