Hypothesis 3A: Youth randomized to AR will (i) Consume less energy from palatable foods in the laboratory test meal; (ii) Report lower levels of LOC eating in the natural environment (based on smartphone data); **Hypothesis 3B:** Youth randomized to AR will demonstrate less weight gain and adiposity compared to youth in control condition at 3-month follow-up.

Exploratory aim #1: Examine whether dose-response effects are present for AB to palatable foods and body composition in participants who receive the AR program at 3 months as a booster compared to those who receive it for the first time.

Exploratory aim #2: Examine the moderating effects of ABs to social threat (reaction times on the visual probe task, neural activation during the MEG session) on intervention effects (AB to food cues, food intake in the laboratory, and body composition).

Exploratory aim #3: Examine the moderating effects of LOC status (LOC vs. No-LOC) on the effects of AR program on “bottom-up” and “top-down” attention circuitry, AB reaction times, food intake, and body composition.

Exploratory aim #4: Examine the moderating effects of race on the effects of the AR program on attention bias, laboratory consumption, and weight/adiposity.

VI. Study Design and Methods

a. Subject Enrollment

A maximum of 120 overweight/obese but otherwise healthy adolescent girls, age 12-17y, (in order to randomize 40 with LOC eating and 40 without LOC eating), will be recruited through mailings to families in the Washington, D.C. greater metropolitan area, a method that has shown success in our previous community-based and intervention studies of youth with LOC eating (40, 43, 47, 58, 100).

Eligibility Criteria

Inclusion Criteria:

Volunteers will qualify if they meet the following criteria:

1. Age between 12 and 17 years (at the start of the study).
2. Female sex.
3. BMI at or above the 85th percentile for age and sex according to the Centers for Disease Control US Standards (101).
4. Right handedness.

LOC sample only:

5. ≥ 1 episodes of LOC eating during the past month prior to assessment, *assessed using a clinical diagnostic interview for eating disorders*

No-LOC sample only:

6. No episodes of LOC eating during the past month prior to assessment, *assessed using a clinical diagnostic interview for eating disorders*

Exclusion Criteria:

Individuals will be excluded (and provided treatment referrals as needed) for the following reasons:

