- d. **MEG Recording.** Brain magnetic fields will be recorded with the 275-channel OMEGA system. Participants will sit in the magnetically shielded recording room with their heads in a helmet covered with 275 SQUID sensors. Head position within the magnetometer will be determined before and after each MEG session by digitizing the position of three indicator coils that are attached to the preauricular and the nasion fiducial points. The positions define the coordinate system for the signals and allow for post-hoc correction of head movement artifacts. Digital photographs of the fiducial points will also be taken to localize the same points on the participant's anatomical MRI scan. Consistent with prior MEG studies in pediatric samples and in populations not previously studied (84, 152), MEG data will be sampled at 600 Hz (bandwidth 0-150 Hz). MEG recording will last for approximately 45 minutes (**Appendix 9**).

5. **Laboratory test meal.** Youth will complete rating scales for hunger, fullness, state mood, and food craving (47, 48). They then receive tape-recorded instructions to “Let yourself go and eat as much as you want” from a multi-array test meal (9,835 kcal). This well-validated paradigm has been used in pediatric (47) and adult (52) studies. Rating scales are repeated post-meal. Consumption is calculated by weighing each item before and after the meal. Energy content and macronutrient composition for each item will be determined according to data from the U.S.D.A. Nutrient Database for Standard Reference and information supplied by food manufacturers. The sample meal is presented in a photograph in **Appendix 12**.

6. An **Anatomical MRI** will be performed on one of the Clinical Center's Phillips 3T scanners (MR2 or MR4). Standard imaging parameters will be used including acquisition of T1 weighted structural images for co-registration (see **Appendix 9** for details on MRI acquisition and preprocessing). If the MRI scanner is not available during participant's

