3. MEG session with the AB Visual Probe Tasks and Eye-Tracking.
4. Laboratory test meal.
5. Eating Disorder Examination (EDE), Version 14.

AR for all: Attention Retraining with EMA in the Natural Environment for 2 Weeks.

Participants will be offered the attention retraining program for two weeks as a “booster.” All participants will receive attention retraining at this point in the study. The attention retraining will be conducted using the same method as in the previous intervention.

Visit #5: Post-AR for all follow-up. This visit will take place 2 weeks after Visit #4, at the end of the 2-week booster attention retraining intervention. All the procedures will be conducted using the same method as in the previous visits:

1. BMI and waist circumference.
2. MEG session with AB Visual Probe Tasks and Eye-Tracking.

Visit #6: 6-month follow-up. This visit will take place approximately 3 months following Visit #5, and/or 6 months following Visit #3. All the procedures will be conducted using the same method as in the previous visits:

1. BMI and waist circumference; a urine sample will be obtained from all participants and tested for pregnancy in postmenarcheal girls.
2. History and physical exam as done in Visit #1 (see **Appendix 14** for follow-up physical exam form).
3. DXA scan.
4. MEG session with AB Visual Probe Tasks and Eye-Tracking.
5. Laboratory test meal.
6. Eating Disorder Examination (EDE), Version 14.

Study Discontinuation and Closure

This study may be temporarily suspended or prematurely terminated if there is sufficient reasonable cause. Written notification, documenting the reason for study suspension or termination, will be provided by the suspending or terminating party to study participants, investigator, funding agency, and regulatory authorities. If the study is prematurely terminated or suspended, the Principal Investigator (PI) will promptly inform study participants, the Institutional Review Board (IRB), and NICHD Clinical Director and will provide the reason(s)

for the termination or suspension. Study participants will be contacted, as applicable, and be informed of changes to study visit schedule.

Circumstances that may warrant termination or suspension include, but are not limited to:

- Determination of unexpected, significant, or unacceptable risk to participants
- Insufficient compliance to protocol requirements
- Data that are not sufficiently complete and/or evaluable

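### Hypothesis 3A(i) concerns palatable-food energy, but the Aim 3 outcome and model use unrestricted meal energy, and 3-month intake has no main-effect arm comparison

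*Combined protocol and SAP*

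**What the plan says.** - **Hypothesis** (Section V, Hypothesis 3A(i)): AR participants will "Consume less energy from palatable foods in the laboratory test meal". No time point is given.
- **Outcome list** (Section VII.c, Specific Aim 3, primary outcomes): "Change in the energy intake at the buffet meal, change in adiposity/body composition (DXA) from the baseline visit to the post-EMA visit".
- **Model** (Section VII.f, Primary Analyses, Specific Aim 3, item 1): "Post-smartphone program lab energy intake from laboratory test meal", analysed by a general linear model or a suitable generalized linear model, "controlling for the baseline visit energy intake and covariates".
- **Objective** (Section IV, Primary objective): "The longer-term effects of AR on AB, neural responding, food intake, and body composition will also be examined at 3-month follow-up".
- **Data** (Section VI.b): at the baseline meal, "Consumption is calculated by weighing each item before and after the meal", and energy content is determined item by item. Later visits use the same methods. The Visit #4 (3-month) procedures include "4. Laboratory test meal".

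**The concern.** There are two separate gaps.

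The first is what is measured. AR trains attention away from pictures of highly palatable food, and the protocol's conceptual figure has it reducing consumption of such food. A girl who eats fewer palatable items and more of the others shows the hypothesised effect, yet her whole-meal energy may change little. The planned model could then report no effect on intake when the effect named in 3A(i) is present. If a palatable subset is defined only after the results are known, the choice of items is open to question.

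The second is when it is measured. The objective names food intake among the 3-month effects, and the 3-month meal is collected. It is also the last meal before every girl is offered AR, so it is the last intake measurement under the randomised AR-versus-control contrast. The Aim 3 primary analyses do not use it.

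**Working it through.** The plan states no figure for this point. Its power statement was derived for Specific Aim 1 and does not decide the matter, so the check is mainly a comparison of texts.

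**Which foods**

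| Place | Quantity |
|---|---|
| Section V, Hypothesis 3A(i) | energy from palatable foods |
| Section VII.c, Aim 3 primary outcome | energy intake at the buffet meal |
| Section VII.f, Aim 3 item 1 | energy intake from the test meal |

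Only the hypothesis carries the restriction. The Food Cue task sorts pictures into high-palatable, low-palatable and non-food, but the available text applies no such sorting to the buffet items. Because items are weighed singly, palatable-food energy can be derived once a list exists.

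**Which visits**

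| Analysis (Section VII.f) | Follow-up visits named |
|---|---|
| Aim 1, lab reaction times | post-smartphone and 3-month |
| Aim 2, neural activity | post-smartphone and 3-month |
| Aim 3, meal energy | post-smartphone only |
| Aim 3, BMI and adiposity | 3-month |
| Exploratory Aim 1, energy intake | post-booster and 6-month |
| Exploratory Aim 3, change in intake (LOC moderation) | post-intervention and 3-month |

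Exploratory Aims 2 and 4 also use energy intake, as moderation analyses with no 3-month time point named for it. Exploratory Aim 1 cannot stand in, because by its visits both groups have been offered AR. So 3-month intake is named only in Exploratory Aim 3, which asks whether the AR effect differs by LOC status, not what the overall arm difference is.

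**Size of the first gap**

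Let D be the fall in palatable-food energy and r the fraction replaced by other foods. The whole-meal effect is D(1 − r). Required sample size is proportional to (SD / effect)². Relative to analysing palatable-food energy directly, the whole-meal analysis needs

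[1 / (1 − r)]² × (SD of whole-meal energy / SD of palatable-food energy)².

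The documents give neither r nor the SDs. With equal SDs (assumed):

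- r = 0: (1 / 1)² = 1.0
- r = 0.25: (1 / 0.75)² = 1.78, about 1.8
- r = 0.50: (1 / 0.50)² = 4.0

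If the SDs differ, each factor is multiplied by the square of their ratio.

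**The case against.** The strongest defence is that whole-meal energy is a legitimate endpoint. Specific Aim 3 is worded broadly, as food intake and body composition, and the outcome list and the model agree with each other on the quantity. The text says energy intake, not total energy intake; reading it as the whole meal is an inference, though a fair one. How far the two quantities diverge depends on the make-up of the buffet, which is shown in an appendix that is not in the available text. If most of the energy comes from palatable items, they may move together. One could also resolve the mismatch by rewording the hypothesis. All of this bears on how much is lost. It does not remove the fact that 3A(i) names a quantity that no outcome or model uses.

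On timing, a reader might infer that the 3-month meal goes unanalysed. The documents do not support that: Exploratory Aim 3 includes change in intake to 3 months, AR versus control. What is absent is a main-effect comparison. A reader might also infer that leaving out 3 months fails Hypothesis 3A(i). It does not, because 3A(i) sets no time point; the conflict is with the objective in Section IV. Nor is Aim 3 confined to intake: it also models daily LOC episodes and 3-month BMI and adiposity, so 3A(ii), 3B and the body-composition part of the objective are covered.

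Finally, this is a pilot sized on Aim 1, so the 3-month gap carries less weight than it would in a confirmatory trial.

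**Conclusion.** The concern holds in two limited parts.

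1. The Aim 3 outcome and intake model do not directly test Hypothesis 3A(i). They use meal energy without restriction to palatable foods, and the available text defines no palatable subset. The cost in required sample runs from none (no replacement) through about 1.8 times (25%) to 4 times (50%). These replacement fractions and the equal SDs are assumptions, so the range illustrates the problem and does not estimate it.
2. The stated objective of examining food intake at 3 months has no main-effect AR-versus-control analysis, although the meal is collected and the Aim 1 and Aim 2 models name both visits.

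No precision gain is claimed for using both meals. Any gain would depend on correlations that the documents do not give, and on the effect lasting to 3 months.

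**What to change.** Before unblinding:

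- List the buffet items that count as palatable.
- Make energy from those items, derived from the weights already planned, the outcome for Hypothesis 3A(i). Keep whole-meal energy as a secondary outcome, and align the outcome list in Section VII.c with this.
- Add the Visit #4 meal to the intake analysis, adjusted for Visit #2 intake, and report the arm difference at each visit. One repeated-measures model would do this, as would separate general linear models for each visit; the choice is not critical.

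The cost is a short item list, revised analysis wording, slightly more analysis work and one additional reported comparison. No new visit, measurement or participant burden is involved.
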